Number of patients Number planned (Statistical design)	
The trial is primarily intended to show superiority but it is also powered to enable a second primary conclusion of non-inferiority using pre-specified hypotheses on the acceptable non-inferiority margin.
 
The sample size calculation uses the following assumptions:
 
 
◆ The patient accrual rate reaches a steady state of 300 patients per year from year 2 of recruitment onwards. During the first year, the yearly accrual rate is assumed to gradually increase quarterly from 76 patients/year (months 1-3), to 124 pts/year (months 4-6), to 174 patients / year (months 7-9), to 227 patients / year (months 10-12).
 
◆ The cumulative rate of patients loss to follow-up is 5% at year 5
 
◆ The trial-level type I error rate is 0.025 1-sided
 
◆ Based on an (unpublished) reanalysis of the data from the 3-year hormone-deprivation therapy arm of EORTC trial 22961, restricted to the subset of patients that had a baseline PSA>10 ng/ml and at least 2 risk factors as specified in the eligibility criteria of the present study, the 5-year progression-free survival rate was 68.7% (95% CI: 62.9%-73.7%). The sample size is thus based on the assumption that the 5-year progression-free survival rate in the comparator arm of this study is 68.5%
 
 
The hypothesis test of superiority of the experimental treatment arm for the primary endpoint progression-free survival is

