	
<math>H_{0\text{superiority}} : HR \geq 1</math> versus <math>H_{1\text{superiority}} : HR < 1</math>
 
The study is sized to have 80% power to reject <math>H_{0\text{superiority}}</math> under the alternative that the true benefit amounts <math>HR=0.708</math> (i.e. +8% at 5 years from anticipated 68.5% at 5 years in the reference arm).
 
The non-inferiority boundary is set at <math>HR=1.159</math> and corresponds to the non-inferiority test
 
<math>H_{0\text{non-inferiority}} : HR \geq 1.159</math> versus <math>H_{1\text{non-inferiority}} : HR < 1.159</math> (i.e. -4% at 5 years)
 
We note that <math>H_{1\text{non-inferiority}}</math> is included in <math>H_{1\text{superiority}}</math>. This justified the closed-testing argument below.
 
With the above specifications, the superiority test requires observing a total of 264 events for the primary endpoint. It is also estimated that with 885 patients entering the study in 3.45 years will provide this number of events, if the total study duration is 7.7 years (i.e. with 4.2 years of follow-up after the entry of the last patient).
 
With this number of events, the study will also have 80% power of rejecting the null hypothesis of inferiority (<math>H_{0\text{non-inferiority}} : HR \geq 1.159</math>) under the alternative assumption of a marginal treatment benefit in favor of the experimental arm amounting <math>HR=0.821</math> (+4.8% at 5 years), using the 1-sided type I error rate of 0.025. By the closed-testing principle, this strategy guarantees strict control of the trial type I error.

Number analyzed	885

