-------------------------	--

	
blood pressure is controlled by anti-hypertensive treatment.
 
 
◆ Prior history of malignancies other than prostate adenocarcinoma (except patients with basal cell, squamous cell carcinoma of the skin), or the patient has been free of malignancy for a period of 3 years prior to first dose of study drug(s). Prior history of bladder cancer excludes the patient.
 
◆ Prior radical prostatectomy (TURP or suprapubic adenectomy for benign prostatic hyperplasia is allowed)
 
◆ Prior brachytherapy or other radiotherapy that would result in an overlap of radiotherapy fields
 
◆ Any contraindication to external beam radiotherapy
 
◆ Patients with significantly altered mental status prohibiting the understanding of the study or with psychological, familial, sociological or geographical condition potentially hampering compliance with the study protocol and follow-up schedule or any condition which, in the opinion of the investigator, would preclude participation in this trial.
 

Treatment
 
Test product, dose and mode of administration
       
Duration of treatment
	
Registered GnRH antagonists, degarelix, will be given at the dose of 240 mg given as two subcutaneous injections of 120 mg at a concentration of 40 mg/mL on day 1, followed by 80 mg given as one subcutaneous injection at a concentration of 20 mg/mL every 28 days (<math>\pm 2</math> days).
 
External beam radiotherapy (EBRT), delivered as one daily fraction, five days a week, started between day 1 and month 6 of the androgen deprivation therapy as per institution policy. The irradiation is the same as in the reference therapy arm. The institution may choose if patient is treated with conventional fractionation or hypofractionation scheme.
 
The minimum duration of androgen deprivation with GnRH agonist or antagonist therapy is 18 months.
 
For each patient, the duration of therapy must be elected upfront by the treating physician among three possible options: 18, 24 or 36 months. The institution shall also declare upfront the duration of the neoadjuvant treatment they intend to deliver to each patient (between 0 and 6 months).

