Statistical methods	
 
◆ Treatment allocation method: No blinding is applied in this study. Before the start of the hormonal therapy, the patients are allocated between the two treatment groups in a 1:1 ratio, by means of stratified blocked randomization with variable block sizes. Stratification factors will be the presence of previous clinical cardiovascular event (no vs yes), the country where the patient is treated, and the number of high risk factors that the patient presents (2 vs >2 high risk factors of relapse)
 
◆ Analysis populations 
 
◆ Intention-to-treat population: All randomized patients will be analyzed in the arm they were allocated by randomization.
 
◆ Per protocol population 1: All patients who are eligible and have received at least 6 months of the allocated treatment
 
◆ Safety population: All patients who have started their allocated treatment (at least one injection of the allocated treatment)
 
◆ Per protocol population 2 (adjusted for switch): All patients who are eligible and have started treatment censoring observations at the time of switching treatment (from GnRH-antagonist to GnRH-agonist) or stopping treatment in absence of progression.
 
 
 
 
Analysis methods:
 
 
◆ The primary analysis of the primary endpoint will be performed in the intent-to-treat population for the superiority test. Two sensitivity analyses will be conducted, repeating the test in the per protocol population 1 and in the per protocol population 2.
 
◆ If the superiority test fails to reject the null hypothesis of no difference a non-inferiority test will be conducted. To protect against the risk of false positive conclusions, the primary test for the non-inferiority question will be conducted in the in the per protocol population 2. The test in the intention-to-treat population and in the per-protocol population 1 will be performed as a first sensitivity analysis. A second sensitivity analysis will be conducted in intent-to-treat population.
 

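### As worded, the primary non-inferiority population censors every event-free patient when planned treatment ends, so the 80% power on 264 events does not carry over to it

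*Protocol*

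**What the plan says.** All references are to the Protocol summary.

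- **Analysis populations (Statistical methods).** Per protocol population 2, labelled as adjusted for switch, contains eligible patients who started treatment, "censoring observations at the time of switching treatment (from GnRH-antagonist to GnRH-agonist) or stopping treatment in absence of progression".
- **Analysis methods (Statistical methods).** If superiority is not shown, "the primary test for the non-inferiority question will be conducted in the in the per protocol population 2". The intention-to-treat population and per protocol population 1 serve as sensitivity analyses.
- **Duration of treatment (Treatment), repeated under Reference therapy.** "For each patient, the duration of therapy must be elected upfront by the treating physician among three possible options: 18, 24 or 36 months".
- **Number of patients (Statistical design).** The superiority test needs 264 events, expected from 885 patients over 7.7 years, with 4.2 years of follow-up after the last entry. The text continues: "With this number of events, the study will also have 80% power of rejecting the null hypothesis of inferiority", against a margin of HR 1.159 (4 points lower at 5 years) if the true HR is 0.821. No separate event count is given for per protocol population 2.

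**The concern.** Treatment has a fixed planned length, so a patient who does well stops treatment without progression. That is the condition on which per protocol population 2 censors. The rule does not distinguish finishing the elected course from abandoning it.

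Applied as written, the rule leaves no completer at risk beyond about 3 years. The margin, however, is expressed as a 5-year difference, and the 264 events depend on follow-up well past that point. The primary non-inferiority comparison would then be close to an on-treatment comparison of progression-free survival, with far fewer events than the power statement assumes. At stake is the second of the two primary conclusions that the trial says it is powered to reach.

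**Working it through.** **Inputs (Number of patients, Statistical design)**
- Error rate: "The trial-level type I error rate is 0.025 1-sided".
- Comparator: "5-year progression-free survival rate in the comparator arm of this study is 68.5" per cent.
- Losses: "The cumulative rate of patients loss to follow-up is 5% at year 5".
- Accrual: "The patient accrual rate reaches a steady state of 300 patients per year from year 2 of recruitment onwards"; in year 1 the quarterly rates are 76, 124, 174 and 227 per year.
- Allocation 1:1, 885 patients, cut-off at 7.7 years, margin 1.159, true HR 0.821.
- Assumed here: constant hazards, and the same HR in per protocol population 2 as in the whole trial.

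**Step 1: reproduce the plan**
- Comparator hazard: −ln(0.685)/5 = 0.0757 per year. Experimental hazard: 0.821 × 0.0757 = 0.0621. Loss hazard: −ln(0.95)/5 = 0.0103.
- Accrual: (76 + 124 + 174 + 227)/4 = 150.25 patients in year 1. The remaining 734.75 at 300 per year take 2.45 years, 3.45 in all, as stated.
- Superiority events: 4 × (1.960 + 0.842)² / (ln 0.708)² = 263.3, rounded up to 264, as stated.
- Expected events at 7.7 years with HR 0.708 and no censoring at treatment stop: 264.9, in line with the plan.
- Non-inferiority power = Φ(ln(1.159/0.821) × √d / 2 − 1.96). With d = 264: 0.3448 × 16.25 / 2 − 1.96 = 0.84, and Φ(0.84) = 80%, as stated.
- At HR 0.821 the same model gives about 280 events at 7.7 years, and 82% power.

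**Step 2: apply the censoring rule as written**

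Every patient has at least 7.7 − 3.45 = 4.25 years to the cut-off, so the cap c (1.5, 2 or 3 years) always comes first and a longer trial adds no events. Expected events = 442.5 × the sum over the two arms of [λ/(λ+η)] × [1 − exp(−(λ+η)c)], where λ is the arm's event hazard and η the loss hazard.

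| Elected duration | Events | Non-inferiority power |
|---|---|---|
| All 18 months | 442.5 × (0.1065 + 0.0883) = 86 | 36% |
| All 24 months | 442.5 × (0.1390 + 0.1157) = 113 | 45% |
| All 36 months | 442.5 × (0.2001 + 0.1675) = 163 | 59% |
| Equal mix (assumed) | 121 | 47% |

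The observed HR must fall below 1.159 × exp(−2 × 1.96/√d). That is about 0.91 with 264 events and about 0.81 with 121. Lengthening each cap by about 3.5 months (start within 2 weeks of randomisation, plus an assumed 3 months of cover from the last depot) raises power only to 41%, 50% and 63%.

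**Step 3: a bound that does not depend on hazard shape**

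At the design rates with HR 0.821, 31.5% and 26.7% have an event by 5 years. Expected events by then are at most 885 × (0.315 + 0.267)/2 = 257.5, about 257. So 264 cannot be expected within 3 years, however the hazard is distributed. Power at this extreme bound would be about 79%.

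**Step 4: the milder reading**

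Suppose that only early stops and switches are censored. Assume that exits are spread evenly over the elected duration and that the durations are equally mixed. The exit rates are assumptions; the protocol gives none.

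| Early exits | Analysed at 7.7 years | Analysed at 264 intention-to-treat events |
|---|---|---|
| 10% | 258 events, 79% | 244 events, 77% |
| 20% | 236 events, 76% | 224 events, 73% |

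Exclusion of ineligible and never-treated patients is not modelled and would lower these figures somewhat.

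**The case against.** The best reply is that the wording is loose but the intent is plain. The population is a per-protocol one, labelled as adjusted for switch. A patient who completes the elected course has followed the protocol, and the rule pairs stopping with switching as if both were departures from it. The text at hand is also a summary that refers to chapters not shown, where the rule may be spelled out. This has force. It makes the point an ambiguity to be closed, and makes the 36% to 59% range conditional on the rule as written. It does not remove the point, because the definition shown governs a primary test and contains no such limit.

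A reader might infer more than the document supports:

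- **That the stated power is unattainable on any reading.** It is not. On the milder reading the loss is a few points, and with few exits there may be none, since about 280 events are expected at 7.7 years with HR 0.821.
- **That this population always has fewer than 264 events.** That follows only if the analysis is triggered at 264 intention-to-treat events and some of those events are dropped. The protocol gives both an event count and a 7.7-year duration.
- **That 36% to 59% is firm.** It assumes a constant hazard. Events concentrated early would raise it, towards 79% at the extreme. Events concentrated after androgen deprivation ends would lower it.
- **That long-term disease control goes unexamined.** The intention-to-treat and per protocol 1 analyses do not censor at treatment stop, so it would be reported, though only as sensitivity analysis.
- **That naming only the antagonist-to-agonist switch biases the test.** The secondary endpoint on switching uses the same direction, and nothing shown indicates that reverse switching is expected or has an effect. It is a matter of consistency only.

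**Conclusion.** The point holds for the definition as written. The primary non-inferiority population censors at any stop of treatment without progression, treatment is planned to stop within 3 years, and the 80% power is carried over from 264 events that arise without that censoring. Under the plan's rates, a constant hazard and HR 0.821, power would be 36% to 59% depending on the elected durations. The shortfall against 264 events does not depend on hazard shape, but its size does. If early stopping alone was intended, what remains is a modest gap: the event count and power for the population actually tested are not stated, and power is likely to be in the 70s if 10% to 20% of patients leave treatment early. Because the rule decides a primary conclusion and the two readings differ so much, the protocol should settle it.

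**What to change.** 1. In the definition of per protocol population 2, state that observations are censored only at a switch or at a stop before the duration elected upfront, and that patients who complete that duration stay under observation for progression-free survival. For consistency, word the switch rule so that it applies alike in both arms.
2. Under Number of patients, give the expected events and the non-inferiority power for per protocol population 2, with the assumed rates of early stopping, switching and exclusion, and say whether the analysis is triggered by 264 intention-to-treat events or by calendar time.

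The cost is wording and possibly a slightly lower stated non-inferiority power. No patients are added and treatment is unchanged. By comparison, keeping the rule as written and restoring 80% power would need roughly 1,440 patients if all elected 36 months, 2,080 if all elected 24, or 2,720 if all elected 18, against 885 planned (265 events needed, divided by the events per patient in step 2 of the working).

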
Criteria for evaluation
 
Efficacy
 
Safety
	
The primary endpoint is progression-free survival defined as the time in days from randomization to death, clinical or biochemical progression, whichever comes first.
 
Where
 
 
◆ PSA progression based on Phoenix definition, i.e. a rise by 2 ng/mL or more above the nadir PSA (Ref. 17) confirmed by a second value measured minimum 3 months later
 
◆ Clinical progression is defined as onset of obstructive symptoms requiring local treatment and demonstrated to be caused by cancer progression or evidence of metastases detected by clinical symptoms and confirmed by imaging
 
◆ Start of another line of systemic therapy in absence of progression
 
◆ Death due to any cause
 
 
Secondary endpoints:
 
 
◆ Clinical progression-free survival
 
◆ Time to next systemic anticancer therapy (including secondary hormonal manipulation)
 
◆ Proportion of patients switching from GnRH antagonists to GnRH agonists and total effective duration of treatment with the originally allocated drug.
 
◆ Overall survival
 
◆ Cancer specific survival
 
◆ PSA at six months after completion of RT
 
 
Safety will be scored by the CTCAE version 4.0. The major safety endpoints in this study are
 
 
◆ the incidence of clinical cardiovascular events – CCE (i.e. arterial embolic or thrombotic events, hemorrhagic or ischemic cerebrovascular conditions, myocardial infarction, and other ischemic heart disease) in patients who had cardiovascular events before entering the trial and in those without such events.
 
◆ Incidence of urinary tract infection
 

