	
 
◆ All secondary efficacy endpoints will be reported in the intent-to-treat population. A sensitivity analysis of the endpoint PSA at 6 months will also be conducted in the per protocol population
 
◆ Safety will be reported in the per protocol population 2 and in the safety population.
 
◆ Quality-of-life and other patient reported outcomes will be reported in the intent-to-treat population
 
◆ Testing strategy for the primary endpoint:  
The 2-sided 95% confidence interval for the hazard ratio for the treatment effect on the primary trial endpoint will be calculated based on a Cox regression model stratified for the stratification factors of the randomization.
 
The test for superiority is conducted first. If it does reject the null hypothesis of no difference (one-sided <math>P < 0.025</math>) then one concludes to superiority of the GnRH-antagonist.
 
If one does not, then the primary test for the non-inferiority question is conducted. If the upper bound of the 2-sided 95% confidence interval around the HR (agonist/antagonist) is <math>< 1.159</math> then one concludes to non-inferiority.
 
Otherwise, one concludes that neither non-inferiority nor superiority of the experimental treatment can be demonstrated compared to the standard treatment.
 
This strategy guarantees full control over the type I error rate of the trial.
 
 
◆ Analysis of secondary endpoints  
The secondary endpoint clinical progression-free survival is also assessed by means of cox regression stratified by the stratification factors of the randomization.
 
The secondary endpoints time to time to next systemic anticancer therapy (including secondary hormonal manipulation) and cancer specific survival are analyzed by means of a Fine-and-Gray model stratified by the stratification factors of the randomization.
 
Quality of life endpoints are analyzed by means of mixed effects regression models adjusted for the stratified by the stratification factors of the randomization. I-PSS scores over time will be reported as change scores from baseline. Health Economic analysis will be done using the scores from the EQ-5D-5L tool (Ref. 39)
 
The other secondary endpoints as well as the main safety endpoints are compared by means of logistic regression models stratified by the stratification factors of the randomization.
 
Other safety parameters are described as frequency tables.
 
 
◆ Interim monitoring
 
◆ No formal interim stopping rule based on efficacy is planned in this study. The central IDMC for the EORTC studies will review the trial at
 

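### In per protocol population 2, cardiovascular events are to be compared by logistic regression, which cannot use that population's censoring; if stopping is similar between arms, this lowers the antagonist arm's event proportion

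*Protocol*

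**What the plan says.** All references are to the Protocol summary.

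- **Endpoint.** Criteria for evaluation, Safety, lists as a major safety endpoint "the incidence of clinical cardiovascular events", in patients with and without such events before entry. Urinary tract infection is the other major safety endpoint.
- **Model.** Statistical methods, Analysis of secondary endpoints: the "main safety endpoints are compared by means of logistic regression models stratified by the stratification factors of the randomization". No time window, offset or handling of incomplete follow-up is given. The same part assigns Cox or Fine-and-Gray models to clinical progression-free survival, time to next systemic therapy and cancer-specific survival.
- **Populations.** Analysis methods: "Safety will be reported in the per protocol population 2 and in the safety population".
- **Censoring.** Analysis populations defines per protocol population 2 as eligible patients who started treatment, "censoring observations at the time of switching treatment (from GnRH-antagonist to GnRH-agonist) or stopping treatment in absence of progression". The safety population is everyone who received one or more injections of the assigned drug, with no cut.
- **Switching and duration.** A secondary endpoint is "Proportion of patients switching from GnRH antagonists to GnRH agonists"; no expected rate is stated. Treatment duration is chosen in advance "among three possible options: 18, 24 or 36 months".

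**The concern.** Censoring has meaning only in an analysis that uses time. In a logistic model each patient is a yes or a no. A patient whose record is closed at a switch, with no event so far, enters as a no with the same weight as one followed for years. The only switch named runs out of the experimental arm, so only that arm can lose observation in this way.

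The effect of the antagonist on cardiovascular events in men at high risk is the first secondary objective listed. Previous cardiovascular event is a stratification factor, and a count of these events can trigger the first IDMC review. A lower event proportion that comes from shorter observation could be read as cardiac protection. No order is set between the two safety populations, so if they disagree the protocol does not say which result counts.

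**Working it through.** **1. The plan's own figures.** No figure is given for the cardiovascular comparison, so the check rests on the design's time frame.
- Primary endpoint events: 4 × (1.960 + 0.842)² / (ln 0.708)² = 263.3, rounded up to 264, as stated.
- Accrual: the first year gives (76 + 124 + 174 + 227)/4 = 150.25 patients. The rest take (885 − 150.25)/300 = 2.45 years, so 3.45 years in all, as stated.
- Follow-up at a 7.7-year cut-off runs from 7.7 − 3.45 = 4.25 to 7.7 years, with a mean of 5.75 over the stated accrual pattern.

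**2. Assumptions not in the document.** The cardiovascular event hazard h is constant, equal in both arms, and 1%, 2% or 5% per year. A fraction s of antagonist patients switches at c = 0.5 or 1 year, unrelated to cardiovascular risk. Stopping is otherwise equal between arms. Death and loss to follow-up are left out.

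**3. Formulas.**
- Uncut patient: p_full = mean of 1 − exp(−h × follow-up)
- Patient cut at c: p_cut = 1 − exp(−h × c)
- Agonist arm: p_full. Antagonist arm: (1 − s) × p_full + s × p_cut
- Expected odds ratio = odds(antagonist)/odds(agonist); it should be 1.00

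**4. Two readings of the stop rule.** The text does not say whether completing the planned course counts as stopping treatment.
- Reading A: it does not count, and non-switchers are followed to the 7.7-year cut-off.
- Reading B: it counts, and both arms end at 18, 24 or 36 months (equal thirds assumed).

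**5. One case in full: h = 0.02, c = 1, s = 0.20, p_cut = 0.0198.**
- Reading A: p_full = 0.1085. Antagonist = 0.8 × 0.1085 + 0.2 × 0.0198 = 0.0908. Odds ratio = (0.0908/0.9092)/(0.1085/0.8915) = 0.82.
- Reading B: p_full = (0.0296 + 0.0392 + 0.0582)/3 = 0.0423. Antagonist = 0.8 × 0.0423 + 0.2 × 0.0198 = 0.0378. Odds ratio = 0.89.

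**6. Range over all assumed h and c.**

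| Switching | Reading A | Reading B |
|---|---|---|
| 2% | about 0.98 | 0.98-0.99 |
| 5% | 0.94-0.96 | 0.96-0.97 |
| 10% | 0.88-0.91 | 0.92-0.95 |
| 20% | 0.77-0.83 | 0.83-0.89 |
| 30% | 0.67-0.74 | 0.75-0.84 |

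**7. Direction when stopping is unequal.** Take Reading B, h = 0.02, 10% switching on the antagonist and 15% early stopping on the agonist, all at 1 year. Antagonist = 0.9 × 0.0423 + 0.1 × 0.0198 = 0.0401. Agonist = 0.85 × 0.0423 + 0.15 × 0.0198 = 0.0390. The odds ratio is about 1.03, now against the antagonist.

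**8. Simulation with no true effect.** There were 4,000 trials per scenario with 442 patients per arm, and switch times were uniform over the planned course. The test was the unadjusted binary comparison at one-sided 2.5%.
- Five-year event risk of 10%, Reading A: switching of 10/20/30% gives a false signal for the antagonist in 6.4/14.8/27.2% of trials.
- Reading B, five-year risk of 10% or 20%, switching of 10-40%: 3.6-16.6%.
- Assumed high-risk subgroup of 130 per arm, same risks and switching: 4.3-31.0% (Reading A) or 2.8-7.3% (Reading B).
- Events per person-time instead of a yes/no outcome: 1.8-2.9% in every scenario.
- No switching: odds ratio 1.00 and a rate of about 2.5%.

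**The case against.** **The safety population is also analysed, and it is not cut.** This stands. A reader might infer that the whole cardiovascular comparison is biased. The document does not support that: follow-up of 4.25 to 7.7 years depends on entry date, which 1:1 randomisation balances. Ignoring time there is a matter of efficiency and preference, not bias under the null.

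**The rule also censors at stopping, in both arms.** This stands too. A reader might infer that the design favours the antagonist by construction. That holds only if stopping is otherwise similar between arms, as step 7 shows. Figures that ignore the stop rule (Reading A alone) are the larger of two possible sizes.

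**Switching may be rare.** Listing the proportion of switchers as an endpoint shows that it will be measured, not that it is large. At 2% the distortion is negligible.

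**The sentence on populations speaks of reporting, and the sentence on logistic regression names no population.** Applying the one to the other is an inference, though the natural one: these are the only populations given for safety and the only model given for its main endpoints. An analysis plan could add a time window or a time-based model. But the protocol fixes both model and population, and a plan that follows it inherits the problem.

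**No formal error rate is breached.** Correct. The 0.025 level is claimed for the primary endpoint, and the cardiovascular objective is worded as documentation. The simulated rates show how often a misleading signal would arise, not a failure of the trial's error control.

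**Conclusion.** The point holds for per protocol population 2. Its censoring rule and the logistic model are incompatible, and applying both gives an odds ratio that mixes event risk with length of observation. With no true effect, similar stopping between arms and switching unrelated to cardiovascular risk, the expected odds ratio falls below 1.00 by an amount that depends on switching. It is barely visible at 2%, about 0.88-0.95 at 10% and about 0.67-0.84 at 30%, taking both readings of the stop rule together. These sizes rest on assumed event and switching rates, and the direction rests on similar stopping. The point does not extend to the uncut safety population when follow-up there is similar between arms, nor to the primary endpoint. The protocol should still be changed, because the endpoint serves a stated objective and neither population is given precedence.

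**What to change.** 1. Name the safety population, with all follow-up kept, as the main population for clinical cardiovascular events.
2. In per protocol population 2, replace logistic regression by an analysis of time to first cardiovascular event: cause-specific Cox or Fine-and-Gray with death as competing event, stratified by the randomisation factors, overall and in the stratum with a previous event. Label it supplementary.
3. Apply the switch censoring rule in that population to both arms, and state whether completing the planned course counts as stopping.
4. Using the same time-to-event model in the safety population is advisable for consistency; it does not correct a bias there.

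The cost is a change of wording and slightly more analysis work, with event dates used instead of yes/no. Sample size, treatment and visits are unchanged. Censoring at a switch still assumes that switching is unrelated to cardiovascular risk, which is a further reason to keep that analysis supplementary.
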